5.1 Number of Subjects

30 patients meeting the MRI entry criteria of an average of up to 2 enhancing lesions per month during baseline. It is expected that 75 patients otherwise meeting the entry criteria will need to be screened by MRI to identify 30 study patients.

5.2 Inclusion Criteria for Pre-Treatment Screening

To be eligible for entry into this study, candidates must meet the following criteria at the time of enrollment. If a washout period becomes necessary, these criteria have to be assessed again at the beginning of the MRI baseline period. An additional assessment of the inclusion criteria follows before the beginning of the treatment (day 1 of stage 1)

- Between the ages of 18 and 65 years, inclusive*
- Females and Males (as no specific gender-related differences are expected, no specific gender distribution is planned. See GCP-V § 7 (2) Nr. 12)
- Subjects with a clinically isolated syndrome (high risk of conversion to MS) as well as subjects with clinically definite relapsing-remitting according to published criteria (50)
- Diseases with similar clinical neurological symptoms (e.g. lues, borreliosis, kollagenosis or vasculitis) have been excluded by differential diagnostics
- Subjects able of giving informed consent
- Signed informed consent
- EDSS score between 0.0 and 5.5, inclusive.

- Patients are clinically stable, i.e. without relapse and not having received steroids within 30 days prior to inclusion
- Patients have either failed standard treatment (interferon beta, glatiramer acetate) by clinical measures or were not eligible for any of the standard treatments available or opted not to start or to continue with any of these treatments

NOTE: The decision not to start or not to continue with any of the standard treatments has to be made by the patient after discussion with an independent neurologist not involved in this study and has to be signed in the informed consent.

* Individuals above 65 years of age and minors will not be included in the study since no experience about the side effect profile of BOSWELAN exists for minors and since MS patients with > 65 years of age are extremely rare, and the disease at this age is often mitigated by other concomitant diseases, e.g. cardiovascular disease.

5.3 Eligibility Criteria for Initiating Therapy

To be eligible to proceed to the treatment phase of the study (Stage 1-4), subjects must have an average of at least 0.5 Gd-enhancing lesions per month over the 4 month pre-treatment baseline period.

Subjects must not have a relapse during 30 days before initiation of treatment. If a relapse occurs during the last 30 days of the pre-treatment baseline period and eligibility MRI criteria are fulfilled, beginning of the treatment (day 1) is delayed for at least so many days that treatment starts not earlier than 30 days after the relapse and not earlier than 60 days in case i.v. corticosteroids had been given.

5.4 Exclusion Criteria

Candidates will be excluded from study entry (pre-treatment screening) if any of the following exclusion criteria exist at the time of enrollment:

Medical History

Abnormal screening/pre-treatment blood tests will be carefully evaluated in any case by the responsible physician. Blood tests exceeding any of the limits defined below will definitely lead to exclusion from the study:

- ALT (SGPT) or AST (SGOT) > three times the upper limit of normal
- Total white blood cell count < 3,000/mm³
- Platelet count < 85,000/mm³
- Creatinine > 1.5 mg/dl

- Serology indicating active hepatitis B or C infection or other chronic liver disease
- Positive pregnancy test, or breast-feeding female
- Nausea/vomiting as a frequent complaint
- History or signs of immunodeficiency
- Concurrent, clinically significant (as determined by the investigator) cardiac, immunological, pulmonary, neurological, renal, and/or other major disease

Treatment History

If prior treatment was received, the subject must have been off treatment for the required period prior to first investigational drug dose (see Table 2).

Table 2: Restrictions on pre-treatments

Agent	Time required off agent prior to enrollment
Glatiramer acetate (Copaxone TM), Interferon beta (Betaferon TM , Avonex TM , Rebif TM)	12 weeks
IV Ig, Azathioprine (Imurek TM), Methotrexate, Cyclophosphamide (Cytosan TM), Mitoxantrone, plasma exchange, Cyclosporine, oral myelin, Cladribine, natalizumab, and other immunosuppressive treatments	24 weeks
Corticosteroids, ACTH	8 weeks

Prior treatment with any other investigational drug or procedure for MS will be evaluated individually by the investigators.

Miscellaneous

- History of alcohol or drug abuse within the 5 years prior to enrollment
- Female subjects who are not post-menopausal or surgically sterile who are not using an highly effective method of birth control. Highly effective is defined as having a failure rate of <1%. Written documentation that the subject is post-menopausal or surgically sterile must be available prior to study start
- Unwillingness or inability to comply with the requirements of this protocol including the presence of any condition (physical, mental, or social) that is likely to affect the subject's returning for follow-up visits on schedule
- Previous participation in this study
- Participation in other pharmaceutical trials during this study or 3 months before
- Patients hospitalized due to juridical or legal regulation
- Known hypersensitivity to BA
- Known contraindications for MRI examinations including hypersensitivity to gadolinium, severe renal insufficiency, a mechanical heart valve or any kind of metallic implants
- Patients with difficulties swallowing up to 12 capsules per day should not be recruited for screening.

6. Study Medication, Description and Allocation

Study drug must be stored in a secure location.

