- MRS (multi-voxel magnetic resonance spectroscopy)
- Neurological measures: Expanded disability status scale (EDSS), SCRIPPS neurological rating scale (SNRS), MS functional composite (MSFC) consisting of 9-HP-test (Nine-Hole-Peg Test), timed 25 foot walk, paced auditory serial addition test (PASAT), Depression scale (Hospital Anxiety and Depression Scale) and a fatigue scale (Fatigue severity scale according to Flachenecker et al.), Hamburg Relapse Assessment Scale (HARAS)
- Immunological parameters
- Biomarker assessment (Cathepsin G activity and PGE₂ levels)

Patient selection: Subjects with clinically isolated syndrome (CIS) fulfilling MRI inclusion criteria (see below) or clinically definite relapsing remitting multiple sclerosis (RRMS) in an active inflammatory phase who either failed standard treatment by clinical measures or were not eligible for any of the standard treatments (e.g. interferon beta, glatiramer acetate) or, after consultation with an independent neurologist, elected not to start or to continue with any of these treatments. Subjects will be enrolled following completion of all pre-screening procedures. After enrollment, subjects will undergo baseline Gd-enhanced MRIs at 4-week intervals prior to the first dose of study drug.

Statistical Plan: Evaluable populations

The primary outcome in the treatment phase (Stage 3) will first compare mean Gd-enhancing lesion number occurring during the 4 month baseline to mean Gd-enhancing lesion number occurring months 5, 6, 7, 8 on treatment in patients treated with a dose of at least 800 mg t.i.d.

A secondary analysis will compare mean Gd-enhancing lesion number occurring over the 4 months of baseline to that occurring during all treatment months on treatment.

Sample size

Based on analyses of a natural history cohort studied with monthly MRIs for a minimum of one year, a baseline-to-treatment designed trial incorporating 4 baseline MRIs and 4 treatment MRIs will require 30 patients to detect a 40% reduction in Gd-enhancing lesions with an alpha of 0.05 (one-sided).

2. Introduction and Study Rationale

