6.2 Enrollment Procedure

Subjects will be enrolled following completion of inclusion and exclusion evaluation, and enrollment will be documented at this point in the patient's file. The patient identification number will serve as identifier for each patient.

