10 SCHEDULE OF EVENTS

10.1 Tests and evaluations

Unless otherwise specified, tests and evaluations described below for the screening visit must be performed within seven days prior to the patient's first MRI. Blood samples should be drawn as early in the day as possible, preferably at the same time of day to avoid diurnal variation and before any steroids are taken in order to avoid depletion of lymphocytes by these agents.

In the event of an MS relapse, a MRI scan will be obtained prior to initiation of steroid therapy. The next scheduled MRI scan will be delayed until at least 28 days after the end of steroid therapy. Subsequent MRI scans will occur at regularly scheduled patient visits.

Additional non-pharmaceutical studies carried out at the discretion of the investigator when deemed appropriate for optimal management of the patient must also be reported.

See Study Schedule Flow Chart (App. A) for summary of tests and evaluations by time-point.

Month -3 (Screening Visit)

Unless otherwise specified, the tests and evaluations described below must be performed within seven days prior to the patient's first MRI in order to determine

patient eligibility:

- A complete medical history.
- A complete MS history.
- Inclusion and exclusion criteria.
- A complete physical examination.
- Vital signs and body weight.
- Haematology: see 11.3.
- Blood chemistries: see 11.3.
- Hepatitis B and C Screening or Check for recent Hepatitis B and C Screening: see 11.3.
- Urinalysis: see 11.3.
- Urine pregnancy test for women of child-bearing potential.
- Recording of concomitant medication.
- EDSS, SNRS, MSFC.
- HAQUAMS, MSIS29, HADS, Fatigue Severity Scale, HARAS for each Relapse within the last 12 months
- Cranial MRI.

Month -2 (\pm 7 days)

- Monitoring of adverse events.
- Vital signs and body weight.
- Urine pregnancy test for women of child-bearing potential.
- Recording of concomitant medication.
- Cranial MRI.
- EDSS, SNRS

Month -1 (\pm 7 days)

- Monitoring of adverse events.
- Vital signs and body weight.
- Urine pregnancy test for women of child-bearing potential.
- EDSS, SNRS, MSFC.
- Recording of concomitant medication.
- Cranial MRI.

Month 0 (\pm 7 days)

- Cranial MRI (within 7 days prior to study drug administration).
- Inclusion and exclusion criteria.
- Monitoring of adverse events.
- Complete physical examination.
- Vital signs and body weight.
- Urine pregnancy test for women of child-bearing potential.
- Haematology: see 11.3.

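### Section 5.4 counts prior-treatment washout back from the first study dose, while the Table 2 it cites counts from enrollment, at least 12 weeks earlier

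*Protocol*

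**What the plan says.** The Treatment History part of Section 5.4 sets the rule as "the subject must have been off treatment for the required period prior to first investigational drug dose (see Table 2". The periods are in Table 2: 12 weeks for glatiramer acetate and interferon beta, 24 weeks for immunosuppressants, natalizumab and similar agents, and 8 weeks for corticosteroids and ACTH. The column that holds them is headed "Time required off agent prior to enrollment".

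The rest of the protocol bears on the anchor as follows:

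- The opening of Section 5.4: "Candidates will be excluded from study entry (pre-treatment screening) if any of the following exclusion criteria exist at the time of enrollment".
- Section 5.2: "If a washout period becomes necessary, these criteria have to be assessed again at the beginning of the MRI baseline period". By implication, a washout ends before the first baseline scan.
- Section 6.2: "Subjects will be enrolled following completion of inclusion and exclusion evaluation".
- Section 10.1, screening visit at month -3: the evaluations "must be performed within seven days prior to the patient's first MRI in order to determine" eligibility.
- Summary, patient selection: "After enrollment, subjects will undergo baseline Gd-enhanced MRIs at 4-week intervals prior to the first dose of study drug".

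Section 5.3 uses the same scans as the gate to treatment: "subjects must have an average of at least 0.5 Gd-enhancing lesions per month over the 4 month pre-treatment baseline period". Sections 3.2 and 14 use them as the reference for the months 5 to 8 scans in the primary efficacy comparison.

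**The concern.** One section gives two starting points for the same washout periods, with the whole MRI baseline between them. The sentence that states the rule in full is the looser of the two. A site could plausibly apply it, because Section 10.1 repeats the inclusion and exclusion check at month 0, just before dosing.

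The trial has no control arm, so each patient's four baseline scans carry the whole comparison. Section 2.1 describes the approved treatments as anti-inflammatory, and Section 9.1 keeps scans at least 28 days clear of corticosteroids. The protocol thus accepts that other drugs can affect the lesion count. If scans fall within the washout that the protocol itself requires, both the baseline mean and the entry decision may reflect the earlier drug or its withdrawal. The population makes this realistic: Section 5.2 admits patients who failed or stopped interferon beta or glatiramer, and it foresees washouts.

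**Working it through.** **Inputs.** Four baseline MRIs at 4-week intervals and a 12-week run-in (Summary). Month 0 MRI at most 7 days before the first dose, and screening at most 7 days before the first MRI (Section 10.1). Washout periods of 84, 168 and 56 days (Table 2: 12, 24 and 8 weeks).

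**Gap between anchors.** First baseline MRI to first dose: (4 − 1) × 4 = 12 weeks, which reproduces the stated run-in. Adding the 7-day screening window and the 7-day window before dosing gives up to 12 + 1 + 1 = 14 weeks from the screening visit. Section 5.2 lets enrollment precede a washout, so 12 weeks is a minimum for the enrollment anchor and the nominal figure for the MRI-baseline anchor.

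**Rule for counting scans.** Take nominal scans at days −84, −56, −28 and 0 relative to first dose. With D days off drug at first dose, a scan on day s is taken D + s days off drug. It lies inside the washout W if D + s < W.

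**Patient exactly at the 5.4 limit (D = W).**

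- Interferon/glatiramer, W = 84: scans at 0, 28, 56 and 84 days off drug, so three of four are inside. With the month 0 scan on day −7, the last is at 77 and all four are inside.
- 24-week agents, W = 168: scans at 84, 112, 140 and 168, so three of four are inside. With the last scan on day −7 (161), all four are.

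**How the count falls as time off drug at first dose grows (nominal schedule).**

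| Scans inside washout | Interferon/glatiramer | 24-week agents |
|---|---|---|
| 3 | 12 to <16 weeks | 24 to <28 weeks |
| 2 | 16 to <20 weeks | 28 to <32 weeks |
| 1 | 20 to <24 weeks | 32 to <36 weeks |
| 0 | 24 weeks or more | 36 weeks or more |

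**Corticosteroids, W = 56.** Read alone, the 5.4 sentence with D = 56 gives 56 − 84 = −28 days at the first scan, meaning steroids could be taken until the second scan. Section 5.2 separately requires 30 steroid-free days before inclusion. With inclusion on the day of the first scan, the scans then fall at 30, 58, 86 and 114 days, so one is inside the 8 weeks. Steroids given for a relapse during the baseline come under Sections 5.3 and 9.1 and are a separate matter.

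**With the first baseline MRI as anchor.** Time off drug at the first scan is at least W, so no scan is inside. Minimum time off drug at first dose becomes 12 + 12 = 24, 24 + 12 = 36 and 8 + 12 = 20 weeks.

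**The case against.** The best defence is that the requirements add up instead of competing. The 5.4 sentence refers to Table 2, the section's opening judges exclusion at enrollment, and eligibility is checked at month -3 and again at month 0. On that view the first-dose wording is only the second check. A patient who meets Table 2 as headed also meets the sentence, so harm needs a site to follow one sentence and overlook the header of the table it cites. This stands as far as intent goes. It does not make the sentence correct, and no text says that both conditions apply.

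Sections 7.5.2 and 7.3.1 also bar Table 2 drugs other than corticosteroids during participation, so a patient could not be on interferon while being scanned. That is right, and it puts the 0-day scan at the edge of what is allowed. But it does not restore the washout. If the last interferon dose came at a screening visit 7 days before the first MRI, the nominal scans fall at 7, 35, 63 and 91 days, and three are still inside 84. Only the four-of-four variant disappears, because a day −7 last scan would then be at 84 days.

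Finally, the counts describe a patient at the limit, and the protocol does not say how many patients will have taken a Table 2 agent. Both points are fair. They limit the weight of the finding but do not remove it.

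**Conclusion.** The concern holds. The 5.4 sentence contradicts the table it cites, by at least 12 weeks, and read alone it admits patients whom that table excludes. At the limit, three of four baseline scans lie inside the required washout for both the 12-week and the 24-week agents. The number falls to none at 24 and 36 weeks off drug at first dose. These counts assume the nominal 4-weekly schedule and a site that applies the sentence instead of the table header.

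No effect on the primary result is shown, since the size and direction of any bias cannot be derived from the protocol. Because the stricter reading is recoverable and workable, this is a correction that should be made, not a flaw that invalidates the design.

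**What to change.** In the Treatment History sentence of Section 5.4, replace the first-dose anchor with *the first baseline MRI (month -3)*, and put the same anchor in the Table 2 header in place of enrollment. This also settles the case in Section 5.2 where enrollment comes before a washout.

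The cost is two wording changes. Against the Table 2 reading, no delay is added, because enrollment comes before the first MRI and screening falls within 7 days of it. Against the first-dose reading, patients stay off treatment about 12 weeks longer before dosing: 24 instead of 12 weeks for interferon or glatiramer, and 36 instead of 24 for the 24-week agents.

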6.1 Study Drug

BOSWELAN will be provided as gelatine capsules containing 400 mg of the frankincense extract.

6.2 Enrollment Procedure

Subjects will be enrolled following completion of inclusion and exclusion evaluation, and enrollment will be documented at this point in the patient's file. The patient identification number will serve as identifier for each patient.

6.3 Drug Accountability

Accurate records will be kept with respect to documenting dates and amount of study drug received, to whom dispensed (subject-by-subject accounting), and

accounts of any study drug accidentally or deliberately destroyed. All unused capsules must be saved for drug accountability.

7. Therapy

7.1 Treatment Schedule

BOSWELAN is provided as capsules containing 400 mg of the frankincense extract.

Patients must be advised to swallow the capsules with a full glass of liquid before or during a meal.

Definition of “not tolerated”: Persisting moderate adverse events at the next dosing time point or whenever the investigator feels that the dose has to be (temporarily) reduced or dosing be omitted.

Definition of “well tolerated”: No or mild adverse events which have resolved before the next dose. Since the definition of the highest well tolerated dose will in most cases be done retrospectively after first moderate or severe adverse events occurred, establishing the highest well tolerated dose will include at least one dose above this dose level. Whenever the definition of “not tolerated” is fulfilled, the dose will be reduced until the “well tolerated” dose is established.

“Dose” is defined as any daily dosing regimen which also allows for different number of capsules at the 3 dosing time points per day.

BOSWELAN will be titrated up to the maximum well tolerated dose or to a maximum of 1600 mg t.i.d (whatever occurs first). The dose titration period will occur over 28 days (stage 1). After determining the maximum well-tolerated dose, each patient will be continued on this dose for another 28 days for dose tolerability and stabilization (stage 2), followed by additional 6 months of treatment (stage 3). Subsequent adjustments to the dose will be made as necessary. Patients are offered to continue drug intake after completing stage 3 during the follow-up stage.

The titration rules for the dose finding period stage 1 of the study are as follows:

A dose increase will be performed only if the previous dose was sufficiently tolerated, i.e. no adverse event or only mild adverse event(s), which has resolved at the next dosing time point.

If an increase in dose is not tolerated, the dose will be temporarily reduced. There should be no more than 3 temporary dose reductions during the dose escalation phase, i.e. after a third dose reduction the dose will be fixed at that or a lower well tolerated dose level.

7.2 Dose Titration Scheme

The dose unit for the following titration scheme has been set as 400 mg/capsule. Dosing is at morning, midday and evening with at least 6 hours between doses.

BOSWELAN will be titrated up to the highest well tolerated dose or to a maximum of 3 x 1600mg during Stage 1.

The dose titration period will be up to 28 days. The dose reached at that time point should be the maximum dose that is well tolerated.

Titration scheme: The dose unit has been set as 400 mg/capsule.

Days	Dosing schedule	Special measures
0	1-0-0	
1:	1-1-1	phone contact on Day 1 before morning dose
2-3	1-1-2	
4-6:	2-1-2	phone contact on Day 4 before morning dose
7-9:	2-2-2	
10-12:	2-2-3	
13-15:	3-2-3	phone contact on day 13 before morning dose
16-18:	3-3-3	
19-21:	3-3-4	
22-24:	4-3-4	
25-28:	4-4-4	

It is expected that adjustments to this schedule will be needed in the event that side effects occur or if dose reductions are necessary. However, patients should remain on each new dose for a minimum of 3 days before the next increase.

Any re-increase of dose after a dose reduction due to an adverse event requires consultation by phone with either the treating physician or the study nurse. In case of a serious adverse event (SAE), dosing will be stopped until the SAE has resolved. Dosing will then resume at a reduced dose level. If dosing is stopped for greater than 2 weeks, the study medication will be stopped in that patient and the patient will be withdrawn prematurely from the study.

Any intolerance of moderate or severe degree must be reported by the patient to either to the treating physician or a study nurse by phone.

The first dose will be administered in the respective Clinical Center. Each patient will contact the study nurse on days 1 (before morning dose), 4 (before morning dose), and on day 13 (before morning dose). Patients will be seen at the center

on days 0 and day 28 and the morning dose will be administered at the center on these days (in case of participating in the pharmacokinetic sub-study).

Treatment of adverse events is at the investigator's discretion.

7.3 Discontinuation of Treatment

If patients are not able to swallow the capsules with water capsules might be put in warm water and solved which takes about 10-15 minutes. As the extract is liquid and the capsule water-solvable this procedure guarantees that the whole amount of the extract is ingested. There is not indication from the manufacturer Alpinia that this procedure will lead to changed pharmacocinetics. However, to avoid heterogeneity within the treated cohort this procedure will be restricted to single cases.

